## 23.2. Health economics analysis

QALYs will be calculated using responses to the EQ-5D-5L, using the "area under the curve" approach. Unit costs will be applied to all healthcare resource use items, and mean resource use (for each category of healthcare usage) and mean total costs will be calculated for all trial participants. The per participant cost of each surgical procedure will also be determined, with the mean cost per type of LFS also estimated. Analysis of productivity losses will use the human capital approach, and the self-reported days of absence will be multiplied by the respondent-specific wage rate. The human capital approach assumes that the value of lost work is equal to the amount of resources an individual would have been paid to do that work, and values productivity losses as a result of morbidity (or mortality) by measuring time lost from work and multiplying this with the gross wage of the person.

The final statistical model for analysis will be selected following data examination and measures of model fit. Multiple imputation will be used to impute all missing values for the EQ-5D-5L and total cost estimates for non-responders. A cost-consequence analysis will initially be reported, describing all the important results relating to costs and consequences (across the full range of clinical outcomes). Incremental cost-utility analysis will then be undertaken to estimate the incremental cost per QALY gained, adjusting for baseline covariates. The robustness of the results will be explored using sensitivity analysis. This will explore uncertainties in the trial-based data itself, the methods employed to analyse the data, the population and the generalisability of the results to other settings. Cost-effectiveness acceptability curves will also be produced to reflect the probability that LFS is cost-effective at different cost per QALY willingness to pay thresholds, compared to BCC.

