#### 9.2. Primary and secondary objectives and outcome measures

The primary outcome is the Oswestry Disability Index (ODI), a validated LBP physical function disability score, at 24 months (also measured at 6 & 12 months). The ODI is well validated and a commonly used outcome measure in LBP RCTs including surgery and contains 10 items that assess domains including personal care, walking, standing and sleeping.

Secondary outcomes include LBP severity (Numerical Rating Scale), measured using monthly SMS data or by email or paper options dependant on participant preference (over 24 months). We will also collect participant reported outcome measures reported via questionnaires at 6, 12 and 24 months. The participant questionnaires include: quality of life (EQ-5D-5L), depression (PHQ8), fear avoidance beliefs (TSK), pain self-efficacy (PSEQ), work outcomes (days-off-work), comparison of back pain from entering the study to timepoint of questionnaire using Global Perceived Effect Scale (GPE), healthcare use (NHS and non-NHS including concurrent treatments ie: analgesia) and treatment satisfaction measured at 24 months follow-up with scoring 0-10 (with 10 being very satisfied with treatment).

Further secondary outcome measures will be collected throughout the 24 months using specially designed CRF's to be completed by clinicians and researchers regarding surgery, Best Conservative Care (BCC), Surgery complications (intra and post operative), further surgery including re-admission, Fusion Failure (LFS participants only), BCC complications.

Objective	Outcome measure	Time point(s) of evaluation of this outcome measure (if applicable)
1. To test for superiority of	Primary:	24 months (also measured at 6
lumber fusion surgery (LFS)	LBP-related physical function	& 12 months)
versus BCC on disability	using the Oswestry Disability	
(physical function) in	Index (ODI version 2.1b)	
patients with persistent		
lower back pain (LBP)		
	Secondary:	
2. To investigate the cost-		
effectiveness of LFS	LBP severity (Numerical	
compared with best	Rating Scale) monthly – post	
conservative care (BCC)	randomisation	
	Participant reported	
	outcomes	

	measured at 6m, 12m and	
	24m post randomisation:	
	1. Quality of Life: EQ-5D-5L	
	2. Pain Self-efficacy	
	Questionnaire (PSEQ)	
	3. Patient Health	
	Questionnaire (PHQ8)	
	4. Tampa Scale of	
	Kinesiophobia (TSK)	
	5. Global Perceived Effect	
	Scale (GPE)	
	6. Healthcare Resources	
	Use	
	7. Work status	
	8. Treatment Satisfaction	

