#### 17.2. Data Collection

## 17.2.1. Baseline

A baseline questionnaire will be completed by participants at a face-to-face appointment, over the telephone, videoconference or via the post. The questionnaire will include the following outcome measures: Oswestry Disability Index (ODI), Quality of life (EQ-5D-5L) only, we have omitted the EQ-VAS scale for this study, Pain Self-efficacy Questionnaire (PSEQ), Patient Health Questionnaire (PHQ8), Tampa Scale of Kinesiophobia (TSK), Work status/work type.

In order to include variables that may be potential moderators of outcome from the treatments offered in the trial, to support future secondary trial analyses of the combined trial datasets from the UK and Australia, we will collect data on the following: smoking, workers' compensation claim, heavy physical demands at work, medication use for LBP, body mass index (Hayden JA et al 2020) via Participant height and weight collected data, duration of LBP, co-morbidities which may include: diabetes, heart problems, high blood pressure, anxiety, depression, stress, neurological conditions, chronic fatigue (ME, Fibromyalgia), COPD, asthma, breathing problems. We will also ask about education, pain following movement, use of a pain mannequin diagram to identify area of pain, low back pain characteristic, severity of low back pain on movement, effects of changing position on low back pain, ethnicity, work status and type.

Information will also be collected if the participant has previously had a discectomy or decompression.

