#### Participant questionnaires

A study questionnaire will be sent to participants for completion at 6-, 12- and 24-months post randomisation. These will be sent by the central study team and can be completed by post or online. The questionnaire will include the following:

- LBP-related physical function using the Oswestry Disability Index (ODI)
- Quality of life (EQ-5D-5L)
- Pain Self Efficacy Questionnaire (PSEQ)
- Change to back pain measure using Global Perceived Effect (GPE)
- Patient Health Questionnaire (PHQ8)
- Fear of movement (fear avoidance) beliefs (TSK)
- Healthcare resources use (NHS and non-NHS) including surgery, conservative care, concurrent treatments (including analgesia)
- Work Status (days off work)
- Participant Intervention Adherence
- Treatment Satisfaction at 24m only

In addition, LBP severity (Numerical Rating Scale) will be collected using monthly SMS messages which will contain a link to enter a score or by email or by paper version via the post (participant preference) to capture data on low back pain severity. A reminder email/SMS message will be sent 2 days after the initial message, sent from the central study team to participants over the 24 months follow-up period. We will follow up with a postal reminder by post (for participants wishing to complete the LBP pain severity on paper) two weeks after the initial postal form was sent to accommodate postal delivery.

All postal questionnaires including LBP pain severity will be accompanied with a self-addressed stamped return envelope.

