# 23.1. Within trial economic evaluation

An economic evaluation will be undertaken alongside the trial to estimate the cost effectiveness of LFS versus BCC. This will take the form of an incremental cost-utility analysis to estimate cost per quality adjusted life year (QALY) and incremental net benefit at 24 months follow-up, using patient level data on costs and outcomes from the trial. The base-case analysis will be from an NHS perspective, with an additional analysis from a societal perspective taking into account out of pocket expenditure and productivity losses. In order to calculate QALYs, the EQ-5D-5L will be included in the questionnaires to participants at baseline, 6, 12 and 24 months. The UK mapping value  set will be applied to participant responses to obtain utility scores, in line with current NICE recommendations.

Data will be collected within the trial to calculate the cost of each LFS undertaken. Information will be collected via the surgery CRF on the type of surgery undertaken and length of stay post-operation and will be used to attach the relevant Healthcare Resource Group (HRG) code from the most recent NHS reference costs. Any additional post-operative resource use will be collected via the participant completed follow-up questionnaires. For each participant allocated to BCC, their package of care will be recorded, including types of care (e.g. a course of physiotherapy, multidisciplinary pain management programme), mode and number of sessions. The per-person cost of BCC will then be calculated.

Information on all other LBP-related resource use will be collected via participant questionnaires at 6, 12 and 24 months. Questions will request information regarding primary and secondary care visits (e.g. GP, nurse, physiotherapy, consultant, specialist, outpatient clinic), visits to other healthcare professionals including non-NHS, prescribed analgesics, tests and investigations, further treatment including surgery and injections. The recall period in each questionnaire will be the previous 6 or 12 months. Unit costs from standard UK sources will be sought for all healthcare resource use items.

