Data on broader costs will also be collected, related to both out of pocket expenditure (e.g. private health care or pain relief items such back supports, TENS machines) and time off work to calculate productivity losses. Information on occupation group and the nature of their employment (full time or part time) will be sought. The average wage for each respondent will be identified using UK Standard Occupational Classification coding and annual earnings data for each broad job type.

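### Productivity loss is set as days of absence times wage, which, read literally, misses working time lost after a participant leaves a job because of back pain

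*Protocol*

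**What the plan says.** The health economics section fixes the productivity calculation in one sentence: "the self-reported days of absence will be multiplied by the respondent-specific wage rate" (Protocol 23.2). The next sentence states the principle more widely. The human capital approach values losses from morbidity or mortality "by measuring time lost from work and multiplying this with the gross wage of the person".

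The inputs named in section 23.1 are "time off work to calculate productivity losses" and, for the wage, the following: "Information on occupation group and the nature of their employment (full time or part time) will be sought".

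The work outcome carries two labels:

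- The prose of section 9.2 calls it "work outcomes (days-off-work"), and the follow-up questionnaire list in section 17.2.3 has "Work Status (days off work").
- The outcome table in section 9.2 lists work status at 6, 12 and 24 months, and Table 2 schedules it at baseline and at those three follow-ups. Section 17.2.1 collects "Work status/work type" at baseline.

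Section 23.1 limits the role of productivity loss: "The base-case analysis will be from an NHS perspective, with an additional analysis from a societal perspective". Section 23 opens by leaving full details to a Health Economic Analysis Plan (HEAP), to be finalised before the final analysis data lock.

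**The concern.** Absence can be reported only by someone who still has a job. A participant who takes 30 days off and returns has 30 days to report. One who gives up work or is dismissed because of back pain can report absence up to that date and has nothing to report afterwards. A participant not working at baseline has no absence at any time, and a return to work would not show either.

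The trial recruits adults aged 18 to 65 with persistent severe low back pain, so leaving work and returning to it are plausible effects of the condition and of treatment. If time after exit contributes nothing, the poorest work outcome lowers an arm's mean days lost. At stake are the comparison of days off work, which is a secondary outcome, and the societal cost-effectiveness analysis.

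**Working it through.** The protocol gives no figure for days off work or productivity loss, so there is nothing to reproduce. The check has two parts.

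**1. The stated rule against the stated principle**

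- Principle (23.2): time lost from work through morbidity or mortality, times gross wage.
- Rule (23.2): self-reported days of absence, times wage.
- Named inputs (23.1): time off work, occupation group, full or part time. No state for having left work is named.

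The two agree while a participant stays employed and part ways at job exit. After exit, working time is still being lost, but no absence can be reported. The rule therefore delivers only part of the principle.

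Section 23.2 calculates mean total costs for all trial participants and imputes total costs for non-responders. A leaver who returns the questionnaire is a responder with no absence to report, so 0 is an easy default. Coding leavers as missing or not applicable would be no better, because it removes people on account of an event after randomisation that treatment may affect.

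**2. Direction and size, on assumed figures**

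None of these inputs comes from the protocol:

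- D = 440 working days in 24 months (220 a year).
- Leavers leave at month 12.
- Those who stay lose s = 20 or s = 60 days over 24 months. Leavers lose s/2 before exit.
- e = proportion leaving, among those employed at baseline.

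Mean days lost per participant:

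- Time after exit scored 0: (1 − e)·s + e·s/2
- Time after exit counted as lost: (1 − e)·s + e·(s/2 + D/2)

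Example with s = 20 and e = 0.20:

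- Scored 0: 0.8 × 20 + 0.2 × 10 = 18.0
- Counted: 0.8 × 20 + 0.2 × (10 + 220) = 62.0

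| s | e | scored 0 | counted as lost |
|---|---|---|---|
| 20 | 5% | 19.5 | 30.5 |
| 20 | 10% | 19.0 | 41.0 |
| 20 | 20% | 18.0 | 62.0 |
| 60 | 5% | 58.5 | 69.5 |
| 60 | 10% | 57.0 | 79.0 |
| 60 | 20% | 54.0 | 98.0 |

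When time after exit is scored 0, the mean falls as more people leave. When that time is counted, the mean rises.

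Between arms, take s = 20 with 5% leaving in one arm and 10% in the other:

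- Scored 0: the arm with more exits looks better by 19.5 − 19.0 = 0.5 day.
- Counted: it is worse by 41.0 − 30.5 = 10.5 days.
- The swing is 0.5 + 10.5 = 11 days, which equals 0.05 × 220.

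The uncounted difference scales with the gap in exit rates and with how early people leave:

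| Exit at | Days uncounted per leaver | 2-point gap | 5-point gap | 10-point gap |
|---|---|---|---|---|
| Month 12 | 12/12 × 220 = 220 | 4.4 | 11 | 22 |
| Month 3 | 21/12 × 220 = 385 | 7.7 | 19.25 | 38.5 |

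If exits are equal in number and timing in the two arms, the between-arm distortion is nil on these assumptions, although both means are still understated.

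**The case against.** A reader might infer that the protocol scores a leaver as zero, so that the worst work outcome is recorded as the best. The text does not say that. No section gives a scoring rule for someone who stops working; zero, missing, not applicable and all working days lost are each open. Even on the literal reading, absence before the exit still counts. That objection stands, and the point is therefore conditional.

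A reader might also infer that job loss is ignored altogether. It is not: work status is a listed outcome at 6, 12 and 24 months and is scheduled in Table 2. It is only the stated productivity formula that makes no use of it. This objection stands too.

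It can further be said that the principle in section 23.2 mentions mortality, which shows that permanent loss of work was meant to be covered, and that the detail is expressly left to the HEAP. This is only partly an answer. The broad principle does not change the narrower rule written beside it, and self-reported absence cannot measure a loss through death. The HEAP need be final only before data lock, by which time participants will have answered questionnaires with 6- or 12-month recall. If the follow-up item asks only for days off work, the reason for leaving and its date cannot be recovered from those answers.

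Finally, the impact is limited and its size is assumed. Both statements are correct. Recovery absence after surgery is also a real cost and not in itself a bias.

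**Conclusion.** The point holds in a limited, conditional form. The written rule captures absence only, so taken literally it omits working time lost after a back-pain-related job exit and does not deliver the principle stated in the same paragraph. The work outcome is also labelled in two ways that are not the same measure.

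If time after exit is scored 0, an arm with more exits would look better on days off work and in the societal analysis. Nothing in the protocol indicates that exits will differ between arms, and no exit rate is given, so the 4.4 to 38.5 days shown above are illustrations and not estimates.

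The ODI primary analysis, the NHS base case and the NHS-perspective extrapolation model are untouched. The change is worth making because it is cheap and because the questionnaire content has to be right before follow-up data accrue.

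**What to change.** 1. **Section 23.2.** For participants employed at baseline, define productivity loss as absence days while employed plus working days not worked after leaving or reducing work because of LBP. Value them at the wage for the baseline occupation, using work status at 6, 12 and 24 months.
2. **Sections 9.2 and 17.2.3.** Reconcile the two labels. Analyse work status at each time point.
3. **Comparison of days.** Make the between-arm comparison among those employed at baseline. Days off among those currently employed should be descriptive only, because restricting to them conditions on an event after randomisation. Report return to work for those not working at baseline.
4. **Questionnaire.** Confirm that the follow-up form records current work status, the reason for leaving and the approximate date.

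The cost is wording in the protocol and HEAP and at most one extra questionnaire item. The drawback is that exit dates will have to be approximated between questionnaires.

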#### Model-based analysis

If the trial shows a positive clinical result for surgical intervention, preliminary decision modelling will also be undertaken to enable extension of the within-trial results beyond 24 months follow-up. The purpose of the model is to extrapolate costs and QALYs over a lifetime time horizon to calculate the long-term cost-effectiveness (cost per QALY) of LFS compared to BCC, from an NHS perspective, with discounting of costs and outcomes at 3.5%. This will be a Markov model which allows the representation of health states related to the condition, recurrence of symptoms and new clinical events e.g. surgery. Full details will be provided in the HEAP.

## 24. DATA MANAGEMENT

The data management aspects of the study are summarised here with details fully described in the study-specific Data Management Plan. See section 28 Participant Confidentiality for information on management of personal data.

#### 24.1. Source Data

Source documents are where data are first recorded, and from which participants' CRF data are obtained. For this study, source data will include the following:

- Hospital records (from which data will be summarised into the CRF)
- Trial specific intervention CRFs
- CT scans
- Participant-reported outcome measures that are submitted directly to the coordinating centre

## 24.2. Location of source data

The location of source data in the study is listed with the tables within the section OBJECTIVES AND OUTCOME MEASURES.

## 24.3. Case report forms (CRFs)

The Investigator and study site staff will ensure that data collected on each participant is recorded in the CRF as accurately and completely as possible. All appropriate data will be transcribed into the CRFs from the relevant source data held in the site medical record(s).

All documents will be stored safely in confidential conditions. On all study-specific documents, other than the signed consent, the participant will be referred to by the study participant number/code, not by name.

## Source data to be recorded directly on the CRFs

CRF entries will be considered source data if the CRF is the site of the original recording (e.g. there is no prior written or electronic record of data).

## 24.4. Non-CRF data

All study data will be recorded on the CRF. No additional data will be held outside of the CRF.

## 24.5. Access to Data

To ensure compliance with regulations, direct access will be granted to authorised representatives from the Sponsor and host institution to permit study-related monitoring, audits and inspections. The data submitted by study participants directly via the clinical database REDCap (i.e. electronic participant reported outcomes) will also be made available to the participating site that recruited the participant; this is detailed within the PIS so that participants are aware of who will have access to this data.

Members of the study team will only be able to access data that they need to, based on their roles and responsibilities within the study.

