#### **Medical notes check**

The central study team will follow up any complications reported by participants with the local research team at participating sites. Details will be collected and recorded on a complications form.

In addition, a final readmission checklist will be undertaken by the research staff on participating site records at 24 months post-randomisation to ensure that all complications data are collected from all participants (i.e. those who had not returned a questionnaire). Data from any readmission events e.g. revision/further surgery identified will be recorded on the Complications Form.

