## **BLINDING AND CODE BREAKING**

Participants and clinicians delivering the interventions will not be blinded to intervention allocation due to the nature of the interventions.

Table 3: provides an overview of the blinding status of all individuals involved in the conduct and management of the study.

Role in study	Blinding status	Additional information
Participants	Not blinded	It is not possible to blind due to the nature of the
		interventions. Participants will be told their treatment
		allocation immediately after randomisation.
Site clinical and	Not blinded	It is not possible to blind due to the nature of the
research staff		interventions. Following randomisation, an email will be
including Principal		sent to the members of the site research team, as
Investigator		applicable, performing the randomisation (as delegated)
		confirming treatment allocation.
Chief	Blinded, except	The Chief investigator will remain blinded to treatment
Investigator(s)	for any SAE	allocation overall (knowledge of treatment allocation is
	causality	limited to participants at their own site). In instances
	assessment.	where serious adverse events are reported, the CIs will
		become unblinded to complete the full causality
		assessment.
Database	Not blinded	The database programmer is responsible for the
programmer		management of RRAMP randomisation system and the
		REDCAP database and will have access to all unblinded
		datasets within both systems.
FORENSIC-UK	Not blinded	Study Management staff within FORENSIC-UK study
Study Management		team will not be blinded to treatment allocations as site
staff within		staff may require support for randomisation, or
FORENSIC-UK study		participants may contact the study team directly. Serious
team		Adverse Event reports will also be handled by the study
		management team which will contain allocation
-		information.
Data Management	Not blinded	Data management staff will have access to the unblinded
		datasets within the study randomisation system and
		database to ensure data quality and undertake central
		monitoring activities.

Table 3: Blinding status of those involved in study	y conduct and management.
---	---------------------------

Study statistician and Senior Study Statistician	Not blinded	The study statistician and senior study statisticians will have access to treatment allocations or data needed for generating the Data Monitoring Committee (DMC) closed reports and the final analysis.

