Health Economist	Not blinded	The costs of the two interventions in this trial are considerably different and thus it will not be possible to blind the health economist.
TSC	Blinded	Will review accruing data and safety overall only, not separated by treatment groups. Full details will be specified in the TSC charter.
DSMC	Not Blinded	DSMC will review accruing data and safety by treatment groups. Allocation may be blinded (arm A or B). Full details will be specified in the DSMC charter and DSMC Report template

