## 24.6. Data Recording and Record Keeping

The case report forms will be designed by members of the study management team which will include the Chief Investigator, study statisticians and study manager.

Data will, wherever possible, be collected in electronic format with direct entry onto the study database by site staff or participants. Electronic data collection has the major advantage of building "data logic" into forms, minimising missing data, data input errors and ensuring the completeness of consent and assent forms. REDCap (Research Electronic Data Capture) is a secure, web-based application designed to support data capture for research studies, providing 1) an intuitive interface for validated data entry; 2) audit trails for tracking data manipulation and export procedures; 3) automated export procedures for seamless data downloads to common statistical packages; and 4) procedures for importing data from external sources.

All data entered will be encrypted in transit between the client and server. All electronic participantidentifiable information, including electronic consent forms, will be held on a server located in an access-controlled server room at the University of Oxford.

The database and server are backed up to a secure location on a regular basis. Details of the data collected, where it is stored and who has access to it along with a fair processing statement will be available for the participants within the study participant information sheet.

Direct access to source data/documents will be required for study-related monitoring and/or audit by the Sponsor, NHS Trust or regulatory authorities as required.

Data captured during phone calls to participants or from paper-based study questionnaires returned to the study office will be entered into the study database by suitably trained central study office staff. Full details of this process will be recorded in the Data Management Plan. Identifiable data will only be accessible by members of the research team with a demonstrated need (managed via access controls within the application) and only used to communicate with the participant (e.g. for study sending follow-up reminders for online form completion or telephone follow-up).

Refer to section 28 for details about retention of participant identifiable data.

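### Section 24.5 opens participants' electronic follow-up scores to the unblinded recruiting site and tells participants so, an avoidable reporting-bias risk for a self-reported primary outcome

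*Protocol*

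**What the plan says.** Section 24.5 states that participants' directly entered data ("i.e. electronic participant reported outcomes) will also be made available to the participating site that recruited the participant"). On disclosure it continues: "this is detailed within the PIS so that participants are aware of who will have access to this data". The section's one general limit is this: "Members of the study team will only be able to access data that they need to, based on their roles and responsibilities within the study".

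Other parts of the protocol bear on how that clause works:

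- **Primary outcome.** Section 9.2 makes the ODI at 24 months, reported by the participant, the primary outcome. GPE and (at 24 months only) treatment satisfaction are in the same questionnaire set.
- **Collection.** On the follow-up questionnaires, section 17.2.3 says: "These will be sent by the central study team and can be completed by post or online". Section 17.3 places reminders and telephone follow-up with the central team.
- **Other response modes.** Under section 24.6, telephone and paper answers are "entered into the study database by suitably trained central study office staff". The site-access sentence does not cover them.
- **Blinding.** "Participants and clinicians delivering the interventions will not be blinded to intervention allocation due to the nature of the interventions". Table 3 also lists site clinical and research staff as not blinded. By contrast, it says of the TSC: "Will review accruing data and safety overall only, not separated by treatment groups".
- **Complications.** The medical notes check has its own route: "The central study team will follow up any complications reported by participants with the local research team at participating sites".
- **Baseline.** Section 15.1 requires the completed baseline questionnaire to be on REDCap before randomisation.

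**The concern.** The protocol keeps outcome collection at a distance from the people who recruit and treat. Section 24.5 partly removes that distance for anyone who answers online, and the participant is told so. Someone who believes that the surgical team may read the answers can shade ratings of disability, change or satisfaction, from gratitude, disappointment or a wish for more help. No reader need actually open the record, because the disclosure alone is enough.

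The shading need not be equal in the two arms. Fusion is done by surgeons working at their own site (section 13.1), so for LFS the recruiting site usually includes the operating team. BCC may be delivered through linked or community services (sections 10.3 and 10.11), so the reader may be less closely tied to the treatment. An unequal shift moves the estimated treatment effect and is not removed by randomisation or by the mixed model.

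The clause also sits awkwardly beside a TSC that sees only pooled data and beside section 22.6, which plans no interim look at the treatment effect.

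**Working it through.** **1. What the text fixes.**

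| Question | Baseline answers | Follow-up answers |
|---|---|---|
| Open to recruiting site if entered online? | Yes (24.5) | Yes (24.5, no limit) |
| Stated site need? | Yes: must be complete before randomisation (15.1) | None stated |
| Paper or telephone answers covered? | No (24.5, 24.6) | No (24.5, 24.6) |
| Date when access opens? | Not stated | Not stated |

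**2. The plan's own figure.** Section 22.2 gives a target difference of 8, SD 18, two-sided 5%, 90% power and 20% loss.

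- Normal formula: n = 2 × 18² × (1.960 + 1.282)² / 8² = 106.4, so 107 per arm; 107/0.8 gives 134 per arm, 268 in total.
- t-based: 107.4, so 108 per arm; 108/0.8 = 135 per arm, 270 in total, as stated.

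The sample size reproduces and is not in question.

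**3. What a net reporting bias would do (illustration).** The protocol gives no size for such a bias, so b is assumed. It is the between-arm difference in reporting shift, averaged over all evaluable participants.

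- SE = 18 × √(2/108) = 2.45 points.
- Type I error = Φ(b/SE − 1.96) + Φ(−b/SE − 1.96).
- Power for a true 8 points when the bias runs against surgery = Φ((8 − b)/SE − 1.96).

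| b (ODI points) | Two-sided type I error | Power, bias against LFS |
|---|---|---|
| 0 | 5.0% | 90.4% |
| 1 | 6.9% | 81.5% |
| 2 | 12.9% | 68.8% |

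These use the unadjusted two-group comparison behind the sample size, not the adjusted mixed model.

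**4. What sites could see while still recruiting.** Inputs: 24 months of recruitment (section 6), a pilot target of 45 in 10 months (10.1), 270 participants and about 20 sites. Assumptions: the remaining 225 arrive evenly over months 10 to 24, everyone answers online, and access opens as data arrive.

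- Reached 6 months by month 24: 45 + 225 × 8/14 = 173.6. Divided by 20 sites and 2 arms, this is 4.3 per arm per site.
- Reached 12 months: 45 + 225 × 2/14 = 77.1, or 1.9 per arm per site.
- Reached 24 months: essentially none.

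Uniform accrual gives 270 × 18/24 = 202.5 and 270 × 12/24 = 135, or 5.1 and 3.4 per arm per site.

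Under the first pattern, the 95% half-width of a site's own arm difference is 1.96 × 18 × √(2/4.34) ≈ 24 points at 6 months and 1.96 × 18 × √(2/1.93) ≈ 36 at 12 months (SD 18 assumed at both). That is several times the 8-point target.

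**The case against.** The best defence has four parts.

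- **The access limit.** The need-to-access sentence can be read as restricting the one before it, and section 24 leaves detail to a Data Management Plan that is not at hand. This could narrow who looks. It does not change what participants are told, and it names no role or time point.
- **Source data.** The paragraph opens with regulatory compliance, and section 24.1 lists participant-reported outcomes sent to the coordinating centre as source data. Electronic entries may have no paper original, so site access could serve oversight. This stands as a reason to keep a controlled route. It does not require recruiting or treating clinicians to see scores.
- **Unblinded anyway.** Participants know their allocation, so expectation bias exists without this clause. That is correct: only the added part is at issue, and the protocol does not allow it to be separated or sized.
- **Response mode.** Mode is the participant's preference, and nothing indicates that it differs by arm. That is also correct; mode only determines who is exposed.

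Some stronger readings are tempting but unsupported. A reader might infer that sites will watch their own results by arm during recruitment. The text does not say when access opens, 24-month ODI and satisfaction could hardly be seen within a 24-month recruitment period, and the visible 6- and 12-month scores would be a handful per arm per site. Some early LFS scores may even precede surgery, since section 9.3 allows for waiting lists. A reader might also infer that the treating surgeon or therapist does read the scores, or that a poor score would prompt further treatment. The protocol states neither. The PIS is not available, so its exact wording cannot be judged.

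**Conclusion.** The point holds as an avoidable design weakness, not as a demonstrated bias. The protocol opens electronically submitted follow-up outcomes to an unblinded site, tells participants so, sets no limit by time point or named role, and gives no use for those scores. With a self-reported primary outcome, this adds a risk of socially desirable answering that may differ by arm and by response mode.

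Size and direction are unknown. The 1- and 2-point cases show only that a small net shift would matter against an SE of 2.45. That the risk may be unequal by arm rests on the inference that the recruiting site is closer to LFS delivery than to BCC delivery. The effect on equipoise is secondary: the visible numbers are too few to inform a recruiter, though they could still sway one. No sample-size figure changes. The point is worth correcting because the remedy is cheap.

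**What to change.** In section 24.5:

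- Limit site access to baseline answers and questionnaire completion status.
- Withhold follow-up participant-reported scores, in every response mode, from recruiting and treating clinicians until at least that participant's 24-month questionnaire is complete, or until database lock.
- Allow an exception for defined safety or source-data oversight needs, handled by delegated staff who neither treat nor recruit.
- Keep the existing central route for complications.

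Change the PIS sentence to match, so that participants know that those who recruit and treat them will not see their follow-up answers during that period.

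The cost is a REDCap user-rights setting, a revised passage in 24.5 and a PIS amendment. Sites lose routine sight of follow-up scores, for which the protocol states no use.
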